2.6 Clinical Studies

2.6.1 Tenofovir Disoproxil Fumarate 300 mg Tablet

Additional safety information from clinical studies on the TDF 300 mg tablet is available in the Viread[®] package insert.¹ Tenofovir disoproxil fumarate PK have been evaluated in healthy volunteers and HIV-1 infected individuals. Tenofovir PK are similar between these populations.

Pharmacokinetics

Tenofovir disoproxil fumarate is a water soluble diester prodrug of the active ingredient tenofovir. The oral bioavailability of tenofovir from TDF in fasted patients is approximately 25%. Following oral administration of a single dose of TDF 300 mg to HIV-1 infected patients in the fasted state, C_{max} are achieved in 1.0 ± 0.4 hrs. Maximum serum concentration and AUC values are 296 ± 90 ng/mL and 2287 ± 685 ng-hr/mL, respectively. The PK of tenofovir are dose proportional over a TDF dose range of 75 to 600 mg and are not affected by repeated dosing. Tenofovir PK are similar in male and female patients.

Safety

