10.4 Sample Size

Sample size/power formulas for a parallel design with two arms (i.e. two different groups of women) can be used to compute sample size/power. Then, this sample size resulting from the assumption of independent groups can be adjusted to reflect that there will be intra-woman correlation in the crossover design. The sample size adjustment can be obtained by this formula:

N' = N (1 - rho)/2

where N' is the sample size for a crossover study, N is the total number of women required in a parallel design with two arms (N/2 in each arm) and rho is the correlation between responses within a single woman during different periods (intra-woman correlation).

For the adherence endpoint, we use preliminary data from HPTN 059 to estimate the standard deviation (SD) of daily gel use and make the assumption that the standard deviations of adherence to daily oral use and of adherence to dual use are similar to that for daily gel use. From the first 4 weeks and the first 8 weeks of daily gel use observed in HPTN 059, we have observed a SD of 11% and 16%, respectively (note that we do not have data in HPTN 059 for the first 6 weeks). Therefore, we use a conservative estimate for the SD for the first 6 weeks of 20%.

To our knowledge, there are no data available for estimating rho. However, it is highly likely that this correlation will be positive and large. The following table gives the power to detect various differences in adherence with a sample size of 144 evaluable women:

	Rho					
	0.0	0.3	0.5	0.7		
Minimum Detectable Absolute						
Difference in Adherence Between Any						
Two Regimens						
2.5%	18%	24%	32%	49%		
5.0%	56%	72%	85%	97%		
7.5%	89%	97%	99%	>99%		

Table 13: Minimum Detectable Difference in Adherence

If there is no intra-woman correlation for adherence, the study will have \geq 89% power to detect absolute differences between the different study drug regimens of at least 7.5% with a two-sided alpha of 5%. Assuming a moderately high intra-woman correlation of 0.5 for adherence, the study will have \geq 85% power to detect an absolute difference of at least 5.0% with a two-sided alpha of 5%.

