2.5%	9%	11%	14%	21%		
5.0%	24%	32%	42%	62%		
7.5%	46%	61%	75%	93%		
10%	70%	85%	94%	>99%		

 Table 14: Minimum Detectable Difference in Condom Use

If there is no intra-woman correlation for condom use, the study will have low power to detect absolute differences in condom use rates of <10% between the different study drug regimens. Assuming a moderately high intra-woman correlation of 0.5 for condom use, the study will have \geq 75% power to detect an absolute difference of at least 7.5% with a two-sided alpha of 5%.

Methods for sample size estimates for the sparse sampling population PK analysis are not available. However, experience indicates that 144 participants, especially when each contributes a pair of specimens the same dosing interval, should provide robust PK parameter estimates.

The more intensive PK sampling to be done at the domestic sites will involve 72 women. Based on data from Gilead in the package insert¹, the coefficient of variation for C_{max} , AUC, and total clearance (CI/F) are 30%, 30%, and 11%, respectively. With 72 participants, assuming no intra-individual correlation, we have 90% power to detect a 0.38 SD unit difference between any two regimens being compared. This represents a 14% difference in C_{max} and AUC and a 5% difference in total clearance (CI/F). If one assumes some correlation within a participant between periods – a very reasonable assumption – these estimates would be even lower. However, because we are using fewer sample points than used in the Gilead tenofovir studies in which the parameter estimates and SDs were determined, we expect that this may increase the variability of the estimates, so we will make no adjustments for intra-participant correlations.

In HPTN 050, blood levels after vaginal tenofovir were too low to allow variance estimates needed for sample size calculations since only one-third of the women had detectable levels of tenofovir in their blood following any given dose. Comparisons of oral and dual formulation arms will rely on imputations of values that are below the assay limits of quantitation which will have the effect of actually reducing the variance of the data which may falsely increase the apparent power of the study design.

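### The PK power figures in section 10.4 contradict each other: at 90% power with no within-woman correlation, 72 women detect about 16% in Cmax and AUC and 6% in clearance, not 14% and 5%

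*Protocol*

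**What the plan says.** PK is one of the two primary objectives (Protocol 3.1). Its quantitative power statement is in section 10.4. The sample is given as "The more intensive PK sampling to be done at the domestic sites will involve 72 women". The variability inputs are coefficients of variation from the oral TDF package insert: for Cmax, "AUC, and total clearance (CI/F) are 30%, 30%, and 11%, respectively".

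The power claim is "With 72 participants, assuming no intra-individual correlation, we have 90% power to detect a 0.38 SD unit difference between any two regimens being compared". The next sentence converts 0.38 SD to a 14% difference in Cmax "and AUC and a 5% difference in total clearance (CI/F)". The section adds that some within-woman correlation is plausible and would reduce these differences. It makes no adjustment for it, because sparser sampling than in the source studies may raise the variability.

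The following paragraph limits the scope for gel: "blood levels after vaginal tenofovir were too low to allow variance estimates needed for sample size calculations".

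Earlier in 10.4 the crossover conversion is N' = N(1 - rho)/2, where "rho is the correlation between responses within a single woman during different periods (intra-woman correlation". A two-sided 5% level is given there for adherence, acceptability and condom use. None is given for PK.

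**The concern.** One statement fixes the sample, the correlation, the power, the detectable difference in SD units and the same difference in percent. Once the CVs are given, the percentage follows directly from the SD figure, yet 0.38 times 30% is not 14% and 0.38 times 11% is not 5%. Separately, 0.38 SD at 90% power looks too small for 72 women at zero correlation under the section's own formula.

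At stake is how sensitive the blood PK comparison is said to be. A reader takes away that a 14% difference in Cmax or AUC is detectable with 90% power before any benefit from correlation. If that is wrong, the stated starting point for a primary objective is too favourable.

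**Working it through.** **Inputs**
- n = 72 women, rho = 0, 90% power, 0.38 SD, 14% and 5% (10.4).
- CV 30% for Cmax and AUC, 11% for clearance (10.4). Section 2.6.1 supports the 30%: "Maximum serum concentration and AUC values are 296 ± 90 ng/mL and 2287 ± 685 ng-hr/mL, respectively", so 90/296 = 30.4% and 685/2287 = 30.0%.
- Two-sided alpha 5%: an assumption for PK, taken from the other endpoints in 10.4.
- Crossover conversion: N' crossover women equal N'/(1 - rho) women per parallel arm. At rho = 0, 72 women equal 72 per arm.

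**1. Check that the method is the protocol's own.** For Table 13 (144 women, SD 20%, difference 5%, rho = 0), SE = 20 × sqrt(2/144) = 2.357 and power = Phi(5/2.357 - 1.96) = 56.4%; the table gives 56%. At rho = 0.5 the method gives 85.1% (table 85%). For Table 14 (SD 34%, difference 10%, rho = 0) it gives 70.4% (table 70%). Every cell of both tables agrees within one point.

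**2. PK, SD unit = parameter SD (the quoted CV), rho = 0.**
- SE = SD × sqrt(2/72) = SD/6.
- Power at 0.38 SD = Phi(0.38 × 6 - 1.96) = Phi(0.32) = 62.6%. With the noncentral t it is 62.0%; a one-sided 5% test gives 73.7%, still not 90%.
- In percent, 0.38 × 30 = 11.4% and 0.38 × 11 = 4.2%.
- Women needed for 90% power at 0.38 SD: 2 × (3.2415/0.38)² = 146.

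**3. PK, SD unit = SD of the within-woman difference.**
- Power = Phi(0.38 × sqrt(72) - 1.96) = Phi(1.264) = 89.7% (paired t 88.9%). This reproduces the stated 90%.
- The difference SD is the parameter SD × sqrt(2(1 - rho)). At rho = 0 that factor is 1.414, so 0.38 SD is 0.38 × 1.414 × 30 = 16.1% and 0.38 × 1.414 × 11 = 5.9%.
- The two SDs are equal only at rho = 0.5, which is not the stated condition.

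**4. What 14% and 5% correspond to at rho = 0.**
- 14/30 = 0.467 SD; power = Phi(0.467 × 6 - 1.96) = 80.0%.
- 5/11 = 0.455 SD; power = Phi(0.455 × 6 - 1.96) = 77.9%.
- Converting 0.38 on the log scale does not recover the stated pair. Cmax/AUC becomes 10.6–11.8% (parameter SD) or 14.6–17.1% (difference SD); clearance becomes 4.1–4.3% or 5.7–6.1%.

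**5. Consistent 90%-power differences for 72 women**, from (1.960 + 1.282) × sqrt(2(1 - rho)/72):

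| rho | parameter SD | Cmax, AUC (× 30%) | clearance (× 11%) |
|---|---|---|---|
| 0 | 0.540 | 16.2% | 5.9% |
| 0.3 | 0.452 | 13.6% | 5.0% |
| 0.5 | 0.382 | 11.5% | 4.2% |

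**The case against.** The strongest reply is that the text never defines its SD unit. On the within-woman-difference reading, 90% at 0.38 SD is correct. That stands. A reader might infer that true power is simply 63% rather than 90%, or that the right percentage is simply 11%, but the document does not support either as the only reading. The reply still does not rescue the paragraph, because on that reading the percentages should be 16% and 6%.

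The practical error is also small. The working claim of 14% at 90% power for Cmax and AUC is met once rho reaches about 0.25 (power 89.9%), and the protocol considers some correlation reasonable. This too stands. It follows that one should not conclude that the margin from correlation is already used up. That is true of 0.38 read as parameter SD, but measured against 14%, correlation above about 0.25 is still a reserve.

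Three further inferences go too far.
- The correction does not change what can be seen for dual versus oral. Gel serum maxima of 3.1–25.8 ng/mL (2.6.2) against an oral Cmax of 296 ng/mL (2.6.1) are about 1–9%, below 11%, 14% and 16% alike.
- The lack of a gel variance is not concealed. The next paragraph of 10.4 discloses it and warns that imputation may inflate apparent power.
- The substudy size is not shown to be wrong. Section 2.7.2 puts all US participants into intensive PK because of sampling needs and technical capacity, not because of this calculation.

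**Conclusion.** Wrong as written. The combination of 90% power, 72 women, zero correlation, 0.38 SD and 14%/5% at CVs of 30%/11% holds on neither reading of the SD unit. The stated percentages fail on both readings, and the corrected figure is the same on both: at 90% power and zero correlation, 0.54 parameter SD, or about 16% in Cmax and AUC and 6% in clearance. The stated 14% and 5% have about 80% and 78% power under those conditions. Sensitivity is therefore modestly overstated, by roughly two percentage points in Cmax and AUC and one in clearance.

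This rests on a two-sided 5% level, which the PK sentence does not give, and on the quoted CVs. Those come from oral TDF, so they support the statement for oral versus dual only. The conclusion concerns a stated figure for a primary objective; it does not show that the trial is too small.

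**What to change.** Replace the power and percentage sentences in 10.4 with:

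> With 72 women contributing both regimens, two-sided alpha 5% and no intra-individual correlation, there is 90% power to detect 0.54 SD of the parameter, about 16% in Cmax and AUC and 6% in CL/F (about 14% and 5% at 80% power). With correlation 0.5 the 90%-power difference is 0.38 SD, about 11% and 4%.

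This wording states the SD unit and alpha. Add that the CVs come from oral TDF, so the statement is supported for oral versus dual only. Keep the sentence saying that positive correlation would lower these differences; it is correct once the figures are truly at zero correlation.

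The cost is a few sentences and a slightly less favourable stated figure. Sample size, endpoints and analysis are unchanged.

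### Intensive-PK power (Section 10.4): with zero correlation, 72 women have about 63% power for 0.38 single-period SD, not 90%, and 0.38 SD does not convert to the stated 14% and 5%

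*Protocol*

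**What the plan says.** Protocol Section 10.4 sizes the intensive PK cohort in a few sentences. On numbers: "The more intensive PK sampling to be done at the domestic sites will involve 72 women". On variability, taken from the package insert, the coefficients of variation for Cmax, "AUC, and total clearance (CI/F) are 30%, 30%, and 11%, respectively". On power, for these 72 women: "assuming no intra-individual correlation, we have 90% power to detect a 0.38 SD unit difference between any two regimens being compared". The conversion follows directly: "This represents a 14% difference in C_{max} and AUC and a 5% difference in total clearance (CI/F".

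The paragraph adds that within-woman correlation would make these differences smaller still. It then says that no correlation adjustment is made, because the sparser sampling may increase variability.

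The start of the same section gives the method for the crossover: N' = N(1 − rho)/2, where N is the total for a two-arm parallel trial. A two-sided alpha of 5% is stated for adherence, acceptability and condom use. The PK sentence gives no alpha and does not say which SD its unit refers to.

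**The concern.** Two things look wrong. First, 0.38 is very close to 3.24/√72 = 0.382. That is the one-sample formula, and in single-period SD units it corresponds to a correlation of 0.5, whereas the sentence says zero. Second, multiplying 0.38 by the stated CVs does not give 14% or 5%.

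Comparing systemic and local PK across the three regimens is a primary objective (Section 3.1), and AUC, Cmax and Cmin are primary endpoints (Section 10.2.1). Section 10.4 says that no sample-size method is available for the sparse-sampling analysis, so this is the only quantitative power statement for PK. A reader who takes it at face value will credit the design with more sensitivity than it has at zero correlation. The same reader will also think that any correlation is entirely in reserve.

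**Working it through.** **Inputs.** n = 72 women, each on all three regimens; rho = 0; CVs of 30% (Cmax), 30% (AUC) and 11% (CL/F); stated result 90% power for 0.38 SD, equated to 14% and 5%. All are from Section 10.4. Section 2.6.1 supports the 30%: 90/296 = 30.4% for Cmax and 685/2287 = 30.0% for AUC. Two-sided 5% is assumed for PK because the section uses it for its other endpoints.

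**Formula.** From N' = N(1 − rho)/2, the standard error of a difference between two regimens is SE = SD × √(2(1 − rho)/N'). Power = Φ(difference/SE − 1.960).

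**Check that this is the protocol's method.**
- Table 13 (SD 20%, n = 144, difference 5%): calculated 56.4%, 71.8%, 85.1%, 97.2% at rho 0, 0.3, 0.5, 0.7. Stated: 56%, 72%, 85%, 97%.
- Table 14 (SD 34%, difference 7.5%): calculated 46.5%, 60.9%, 75.4%, 92.7%. Stated: 46%, 61%, 75%, 93%.
- The remaining cells also agree to rounding.

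**Power for 0.38 SD with 72 women (single-period SD units).**
- rho = 0: SE = √(2/72) = 0.1667; 0.38/0.1667 − 1.960 = 0.320; power = 62.6% (61.4% by the paired t test).
- rho = 0.5: SE = √(1/72) = 0.1179; power = 89.7%.
- One-sided 5% at rho = 0: 73.7%.
- At rho = 0, 90% power for 0.38 SD would need about 146 women.

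**Detectable difference with 72 women, two-sided 5%.**

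| Power | rho | SD units | Cmax, AUC (CV 30%) | CL/F (CV 11%) |
|---|---|---|---|---|
| 90% | 0 | (1.960 + 1.282) × 0.1667 = 0.540 | 16.2% | 5.9% |
| 80% | 0 | (1.960 + 0.842) × 0.1667 = 0.467 | 14.0% | 5.1% |
| 90% | 0.5 | (1.960 + 1.282) × 0.1179 = 0.382 | 11.5% | 4.2% |

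**Converting 0.38 SD to percentages.**
- As single-period SDs: 0.38 × 30% = 11.4% and 0.38 × 11% = 4.2%. On the log scale these are 11.8% and 4.3%.
- As SDs of the within-woman difference at rho = 0: 0.38 × √2 = 0.537 single-period SD, which is 16.1% and 5.9%. On the log scale these are 17.1% and 6.1%.
- Working back from the text: 14/30 = 0.467 SD, with 80% power at rho = 0, and 5/11 = 0.455 SD, with 78%.

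No version gives 0.38 SD, 90% power, 14% and 5% together at rho = 0. One-sided 5% at 90% power comes near on the percentages (0.488 SD, so 14.6% and 5.4%) but not on 0.38.

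**The case against.** **The SD unit is undefined.** If it means the SD of the within-woman difference, 90% power for 0.38 is right (89.7%). This stands as a reading of that one sentence, so the 63% figure applies only to single-period SDs. It does not save the paragraph: the CVs used for the conversion are single-period figures, and at rho = 0 this reading leads to 16% and 6%.

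**The origin of 14% and 5%.** A reader might infer that they are an 80%-power result carrying the wrong label. The numbers fit, but the documents do not show it. They fit equally well a leftover from a 48-woman cohort: 3.24/√48 = 0.468, giving 14.0% and 5.1%. Table 12 still lists four groups of 12, and Sections 7.8.3 and 10.5 still refer to two sites although Section 4.8 names four in the US. The origin is unknown.

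**The 11% CV for CL/F.** A reader might infer that it is impossible, because at a fixed oral dose CL/F is dose divided by AUC and should vary about as much as AUC. That requires both CVs to come from the same subjects, which the protocol does not say, and Section 2.6.1 gives no CL/F figure to check. CL/F is also not a listed PK endpoint. This supports a query to the source and no more.

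**The practical effect is small.** This largely stands. At 90% power and rho = 0, the detectable difference in AUC and Cmax moves from 14% to 16%. Oral and vaginal blood levels differ by more than tenfold on the protocol's figures (Cmax about 296 ng/mL in Section 2.6.1, against maximum gel levels of 3.1 to 25.8 ng/mL in Section 2.6.2). Among the blood-exposure contrasts, oral versus dual use is therefore the sensitive one. Section 10.4 itself warns that imputing values below the assay limit may overstate apparent power.

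**Conclusion.** The statement is wrong as written, because on every reading at least one of its figures fails. In single-period SD units at rho = 0, power for 0.38 SD is about 63% rather than 90%, and the 90%-power difference is 0.54 SD, or 16% in Cmax and AUC. Read as SDs of the difference, the power is right but the percentages should be about 16% and 6%. No other section corrects this.

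The conclusion rests on two-sided 5% and on the protocol's own crossover formula.

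Two stronger conclusions are not supported. The first is that 72 women are too few. Section 10.4 expects positive correlation, and 14% has about 90% power once rho reaches roughly 0.25: SE = √(2 × 0.75/72) = 0.144, and 0.467/0.144 − 1.96 is about 1.27. The second is that no reserve exists for sparser sampling. Correlation does provide one at honest rho = 0 figures; the trouble is that 0.38 SD, in single-period units, already uses a correlation of 0.5.

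Severity is moderate: a power statement for a primary endpoint is wrong, but neither n nor the analysis changes.

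**What to change.** Replace the power and conversion sentences in Section 10.4 with one consistent set that states alpha and defines the SD unit. For example:

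> With 72 women, two-sided alpha of 5% and no intra-woman correlation, there is 90% power for a difference of 0.54 single-period SD (16% in Cmax and AUC) and 80% power for 0.47 SD (14%). At a correlation of 0.5 there is 90% power for 0.38 SD (11%).

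Recompute the CL/F figure (5.9% at 90% power and rho = 0, if the CV is 11%) or drop it. If it is kept, check the 11% against the package insert, because it sits oddly beside 30% for AUC.

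The sentence on making no correlation adjustment can stay, since it becomes true once the zero-correlation figures are given.

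The cost is protocol wording only. The detectable differences at zero correlation become less favourable, and the sample size of 72 is unchanged.

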10.5 Randomization Procedures

Randomization to product sequence will be stratified by site. Within each site, participants will be randomly assigned to one of six study sequences outlined in Table 15: Study Regimen below. In an unblinded trial, special care needs to be taken to assure that the study staff cannot control or guess assignment. The MTN Statistical and Data Management Center will coordinate the randomization procedures, which will be specified in the SSP Manual.

Table 15:	Stuc	dy Re	egimen	

	N	Period 1: 6 WEEKS	1 WK Wash -out	Period 2: 6 WEEKS	1 WK Wash- out	Period 3: 6 WEEKS	1 WK Wash- out
Sequence A	24	Oral		Vaginal		Oral + Vaginal	
Sequence B	24	Vaginal		Oral		Oral + Vaginal	
Sequence C	24	Oral + Vaginal		Oral		Vaginal	
Sequence D	24	Oral + Vaginal		Vaginal		Oral	
Sequence E	24	Oral		Oral + Vaginal		Vaginal	
Sequence F	24	Vaginal		Oral + Vaginal		Oral	

Assignment to end of study period non-intensive PK sample timing will correspond to product sequence randomization for simplicity. For the intensive PK cohorts at domestic sites, the end of study period sample timing will require a second randomization which will be stratified within each of the two sites.

10.6 Participant Accrual, Follow-up, Retention, and Replacement

The accrual period will be 6 months. Up to 204 women may be enrolled to reach the target of 144 evaluable women, where evaluable women are women who have at least one follow-up visit with adherence data in each of the 3 periods of the study. Five of the 7 participating sites will recruit and enroll 24 evaluable participants each, and 2 of the participants sites will enroll 12 evaluable participants each for a total of 144 evaluable participants. The need to enroll replacement participants for enrollees will be dependent on whether the enrollee had at least one full period of the study with no follow-up adherence data. Details on procedures for participant replacement are outlined in the SSP Manual.

Each participant will be followed for 21 consecutive weeks (three periods of 7 weeks). In a crossover study, it is important to have completeness of the data such that the target retention should be set at 100%. Therefore, once a participant has enrolled in the study, the study site will make every reasonable effort to retain her for the entire study period so that she is evaluable. A maximum of 5% loss-to-follow-up of enrolled participants is targeted.

10.7 Data Monitoring and Analysis

10.7.1 Study Monitoring Committee (SMC)

No Data and Safety Monitoring Board oversight is planned for this study. The MTN SMC will conduct interim reviews of study progress, including rates of participant accrual, retention, completion of primary and main secondary endpoint assessments, and study or lab issues. These reviews will take place approximately every 4-6 months, or as needed. At the time of these reviews, or at any other time, the SMC may recommend that the study proceed as designed, proceed with design modifications, or be discontinued.

